#### 8.4.2 Method of Detecting AEs, SAEs, and Other Reportable Safety Events

Care will be taken not to introduce bias when detecting AEs and/or SAEs and other reportable safety events. Open-ended and nonleading verbal questioning of the participant is the preferred method to inquire about AE occurrence.

#### 8.4.3 Follow-up of AE, SAE, and Other Reportable Safety Event Information

After the initial AE/SAE report, the investigator is required to proactively follow each participant at subsequent visits/contacts. All AEs, SAEs, and other reportable safety events, including pregnancy and exposure during breastfeeding, ECIs, cancer, and overdose will be followed until resolution, stabilization, until the event is otherwise explained, or the participant is lost to follow-up (as defined in Section 7.3). In addition, the investigator will make every attempt to follow all nonserious AEs that occur in randomized participants for outcome. Further information on follow-up procedures is given in Appendix 3.

#### 8.4.4 Regulatory Reporting Requirements for SAE

Prompt notification (within 24 hours) by the investigator to the Sponsor of SAE is essential so that legal obligations and ethical responsibilities toward the safety of participants and the safety of a study intervention under clinical investigation are met.

The Sponsor has a legal responsibility to notify both the local regulatory authority and other regulatory agencies about the safety of a study intervention under clinical investigation. The Sponsor will comply with country-specific regulatory requirements and global laws and regulations relating to safety reporting to regulatory authorities, IRB/IECs, and investigators.

Investigator safety reports must be prepared for SUSARs according to local regulatory requirements and Sponsor policy and forwarded to investigators as necessary.

An investigator who receives an investigator safety report describing an SAE or other specific safety information (eg, summary or listing of SAEs) from the Sponsor will file it along with the IB and will notify the IRB/IEC, if appropriate according to local requirements.

Note: To meet EU CTR requirements, the Sponsor will report SUSARs to the Eudravigilance database via E2B(R3) electronic ICSR form in compliance with CTR 536/2014.

#### **8.4.5 Pregnancy and Exposure During Breastfeeding**

Although pregnancy and infant exposure during breastfeeding are not considered AEs, any pregnancy or infant exposure during breastfeeding in a participant (spontaneously reported to the investigator or their designee) that occurs during the study are reportable to the Sponsor.

All reported pregnancies must be followed to the completion/termination of the pregnancy.

Any pregnancy complication will be reported as an AE or SAE.

The medical reason (example: maternal health or fetal disease) for an elective termination of a pregnancy will be reported as an AE or SAE. Prenatal testing showing fetus will be born with severe abnormalities/congenital anomalies that leads to an elective termination of a pregnancy will be reported as an SAE for the fetus.

Pregnancy outcomes of ectopic pregnancy, spontaneous abortion, missed abortion, benign hydatidiform mole, blighted ovum, fetal death, intrauterine death, miscarriage, and stillbirth must be reported as serious events (Important Medical Events). If the pregnancy continues to term, the outcome (health of infant) must also be reported.

#### **8.4.6 Disease-related Events and/or Disease-related Outcomes Not Qualifying as AEs or SAEs**

Efficacy endpoints as outlined in this section will not be reported to the Sponsor as described in Section 8.4.1.

Specifically, the suspected/actual events covered in this exception include any event that is disease progression of the cancer under study.

The Sponsor will ensure that unblinded aggregated efficacy endpoint events and safety data to safeguard the participants in the study.

#### **8.4.7 Events of Clinical Interest**

Selected serious and nonserious AEs are also known as ECIs and must be reported to the Sponsor.

Events of clinical interest for this study include:

- An overdose of Sponsor's product, as defined in Section 8.5.
- An elevated AST or ALT lab value that is greater than or equal to 3X the upper limit of normal and an elevated total bilirubin lab value that is greater than or equal to 2X the upper limit of normal and, at the same time, an alkaline phosphatase lab value that is less

than 2X the upper limit of normal, as determined by way of protocol-specified laboratory testing or unscheduled laboratory testing.\*

\*Note: These criteria are based upon available regulatory guidance documents. The purpose of the criteria is to specify a threshold of abnormal hepatic tests that may require an additional evaluation for an underlying etiology. The study site guidance for assessment and follow up of these criteria can be found in the Investigator Study File Binder (or equivalent).

## 8.5 Treatment of Overdose

For the purpose of this study, an overdose of MK-7684A will be defined as any dose exceeding 3 times or 300% the prescribed dose. For pembrolizumab, an overdose will be defined as any dose  $\geq 1000$  mg. No specific information is available on the treatment of overdose of pembrolizumab or MK 7684A. In the event of overdose, the participant should be observed closely for signs of toxicity. Appropriate supportive treatment should be provided if clinically indicated.

## 8.6 Pharmacokinetics

### 8.6.1 Blood Collection for Serum MK-7684 and Pembrolizumab

CCI [REDACTED]

#### 8.6.1.1 Blood Collection for PK

CCI [REDACTED]

[figure not shown]
#### 8.6.1.2 Blood Collection for Antidrug Antibodies

CCI [REDACTED]

[figure not shown]
## 8.7 Pharmacodynamics

CCI [REDACTED]

[figure not shown]
## 8.8 Biomarkers

### 8.8.1 Planned Genetic Analysis Sample Collection

## 8.9 Future Biomedical Research Sample Collection

## 8.10 Medical Resource Utilization and Health Economics

All-cause hospitalizations and emergency room visits must be reported in the eCRF, from the time of treatment allocation/randomization through 90 days after cessation of study intervention, or 30 days after cessation of study intervention, if the participant initiates new anticancer therapy, whichever is earlier.

## **8.11 Visit Requirements**

Visit requirements are outlined in Section 1.3. Specific procedure-related details are provided in Section 8.

### **8.11.1 Screening**

Written consent must be obtained prior to performing any protocol-specific procedure. Results of a test performed prior to the participant signing consent as part of routine clinical management are acceptable in lieu of a screening test if performed within the specified time frame. Screening procedures are to be completed within 28 days prior to the first dose of study intervention except for the following:

- Laboratory tests are to be performed within 10 days prior to the first dose of study intervention. An exception is hepatitis testing which may be done up to 28 days prior to the first dose of study intervention.
- Evaluation of ECOG is to be performed within 7 days prior to the first dose of study intervention.
- For WOCBP, a serum pregnancy test will be performed within 72 hours or a urine pregnancy test within 24 hours prior to the first dose of study intervention. If urine pregnancy results cannot be confirmed as negative, a serum pregnancy test will be required (performed by the local study site laboratory). Additional pregnancy testing can be conducted if required by local regulations or clinically indicated.
- Archival tumor sample collection is not required to be obtained within 28 days before the first dose of study intervention. Newly obtained tumor tissue may be obtained according to the Procedures Manual.

Participants may be rescreened after initially failing to meet the inclusion/exclusion criteria. Results from assessments during the initial screening period are acceptable in lieu of a repeat screening test if performed within the specified time frame and the corresponding inclusion/exclusion criteria is met. Participants who are rescreened will retain their original screening number.

### **8.11.2 Initial Treatment Period**

Visit requirements are outlined in the SoA (Section 1.3). Specific procedure-related details are provided in Section 8.1.

### **8.11.3 Second Course Treatment Phase**

See Section 6.6.3 for details concerning Second Course Treatment.

#### **8.11.4 Participants Discontinued From Study Intervention but Continuing to be Monitored in the Study**

Participants who discontinue study treatment due to disease recurrence or start of a new anticancer therapy will have Safety Follow-up and then proceed directly to Survival Follow-up Phase as described in Section 8.11.5.

The Discontinuation Visit should occur at the time study intervention is discontinued for any reason. If the Discontinuation Visit occurs 30 days from the last dose of study intervention, at the time of the mandatory safety follow-up visit, the Discontinuation Visit procedures and any additional Safety Follow-up procedures should be performed.

#### **8.11.5 Posttreatment Visit**

##### **8.11.5.1 Safety Follow-up Visit**

The mandatory Safety Follow-up Visit should be conducted approximately 30 days after the last dose of study intervention or before initiation of a new anticancer treatment, whichever comes first.

Participants who are eligible for retreatment with pembrolizumab or MK-7684A may have up to 2 safety follow-up visits: 1 after the Initial Treatment or First Course and 1 after the Second Course.

##### **8.11.5.2 Efficacy Follow-up Visits**

Participants who complete the protocol-required cycles of study intervention or who discontinue study intervention for a reason other than disease progression will begin Efficacy Follow-up and should be assessed every 12 weeks to monitor disease status. Every effort should be made to collect information regarding disease status until the start of new anticancer therapy, disease progression, death, end of study. Information regarding poststudy anticancer treatment will be collected if new treatment is initiated. Participants who completed all efficacy assessments and/or will not have further efficacy assessments must enter Survival Follow-up.

Participants who are eligible to receive retreatment with pembrolizumab or MK-7684A according to the criteria in Section 6.6.3 will move from the Efficacy Follow-up Phase to the Second Course Phase when they experience disease progression. Details are provided in the SoA (Section 1.3) for retreatment with pembrolizumab.

##### **8.11.5.3 Survival Follow-up Contacts**

Participant survival follow-up status will be assessed approximately every 12 weeks to assess for survival status until death, withdrawal of consent, or the end of the study, whichever occurs first.

The first survival follow-up assessment should be scheduled as described below:

- For participants who discontinue treatment intervention and who will not enter Efficacy Follow-up, the first survival follow-up contact will be scheduled 12 weeks after the Discontinuation Visit and/or Safety Follow-up Visit (whichever is last).
- For participants who completed assessments in Efficacy Follow-up, the first survival follow-up contact will be scheduled 12 weeks after the last efficacy assessment follow-up visit has been performed.

#### **8.11.6 Survival Status**

To ensure current and complete survival information (vital status) is available at the time of database locks, updated vital status may be requested during the study by the Sponsor. For example, updated vital status may be requested before but not limited to, an eDMC review, interim and/or final analysis. Upon Sponsor notification, all participants who do not/will not have a scheduled study visit or study contact during the Sponsor-defined period will be contacted for their vital status.

## 9 KEY STATISTICAL CONSIDERATIONS

Upon receipt of investigator letter detailing discontinuation of the MK-7684A clinical program, the following changes apply. The changes listed below supersede any protocol content/instructions from previous amendments.

- This study is closed to enrollment. This study has enrolled 1264 participants.
- This study will be unblinded.
- The estimated duration of study was updated from 6 years to 5 years.
- Participants receiving MK-7684A will be transitioned to pembrolizumab.
- Pembrolizumab can be sourced locally or centrally.
- Participants with access to approved SOC (eg, immunotherapy, chemotherapy, targeted therapy, as monotherapy or in combination) should be considered for discontinuation from the study. Those benefiting from pembrolizumab with, but unable to access it as SOC outside the study, may continue on study and receive treatment with pembrolizumab until discontinuation criteria are met. The final required study visit will be the Safety Follow-up Visit.
- Imaging scans should no longer be submitted to iCRO nor read by BICR. However, for participants who are still on study treatment and deriving clinical benefit and will continue study treatment until criteria for discontinuation are met, local tumor imaging should continue per local SOC schedule and local SOC method of assessment of imaging. All imaging as well as relevant objectives and endpoints will be assessed locally.
- PK/ADA samples will no longer be collected.
- Biomarker FBR samples will no longer be collected.
- ePROs will no longer be collected.
- Treatment beyond progression will no longer be offered. Any participant already receiving treatment beyond progression will be able to complete treatment as planned.
- Participants who complete study treatment or otherwise meet EOT criteria will be discontinued from the study after the EOT visit and any required safety follow-up visit.
- The futility interim analysis (IA1) was conducted. The pre-specified efficacy interim analysis (IA2) and final analysis outlined in the SAP will not be conducted.
- Selected analyses of safety and endpoints will be performed at the end of the study.
- There will be no follow-up for survival status. Participants currently in imaging follow up should obtain imaging and further oncological care as per local standard of care. However, standard safety reporting should continue, as applicable.
- Those participants remaining on study at the time of Amendment 06 should continue to be monitored in the study through the AE reporting period (Section 8.4).

- Participants may enroll in an extension study, if available.
  - Participation in this study is ended when the participant is consented for an extension study.
  - The overall study ends when the last participant completes the last study-related contact, withdraws consent, or is lost to follow-up (Section 7.3), or the last participant on active treatment is consented in an extension study
  - For participants who enter an extension study, all AEs, SAEs, and other reportable safety events must be reported by the investigator in this protocol (parent study) from the time of intervention randomization up to the time of providing documented informed consent for an extension study. Note: Once consented to an extension study, safety events, including those considered related to study intervention, will be collected as instructed in the extension study.

Existing protocol content is retained for historical reference.

This section outlines the statistical analysis strategy and procedures for the study. If, after the study has begun, but prior to any unblinding/final database lock, changes are made to primary and/or key secondary hypotheses, or the statistical methods related to those hypotheses, then the protocol will be amended (consistent with ICH Guideline E-9). Changes to exploratory or other nonconfirmatory analyses made after the protocol has been finalized, but prior to unblinding/final database lock, will be documented in a supplemental SAP (sSAP) and referenced in the Clinical Study Report (CSR) for the study. Post hoc exploratory analyses will be clearly identified in the CSR. Separate analysis plans (ie, separate documents from the sSAP) will be developed to detail PK and biomarker analyses. The ePRO analysis plan will be included in the sSAP.

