#### Secondary

- **Progression-free survival (PFS)**

PFS is defined as the time from randomization to the first documented disease progression per RECIST 1.1 by BICR or death due to any cause, whichever occurs first.

- **Objective Response (OR)**

OR is defined as a confirmed CR or PR per RECIST 1.1 based on BICR.

- **Duration of Response (DOR)**

For participants who demonstrate confirmed CR or PR, DOR is defined as the time from the first documented evidence of CR or PR until disease progression or death due to any cause, whichever occurs first.

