### 9.6.1 Statistical Methods for Efficacy Analyses

This section describes the statistical methods that address the primary and secondary objectives. Methods related to exploratory objectives will be described in the sSAP.

The stratification factors used for randomization (see Section 6.3.2) will be applied to all stratified analyses, in particular, CCI [REDACTED]

[REDACTED] In the event that there are small strata, for the purpose of analysis, strata will be combined to ensure sufficient number of participants, responses and events in each stratum. Details regarding the pooling strategy will be prespecified in the sSAP prior to the database lock for the first efficacy interim analysis, and decisions regarding the pooling will be based on a blinded review of response and event counts by stratum.

The efficacy analyses for PFS, OR, and DOR will include documented progression events and responses that occur prior to Second Course treatment.

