#### 9.6.1.1 Overall Survival (OS)

The nonparametric Kaplan-Meier method will be used to estimate the overall survival curves in each treatment group. CCI [REDACTED]

[REDACTED] The stratification factors used for randomization (see Section 6.3.2) will be applied to both the stratified log-rank test and the stratified Cox model. Participants without documented death at the time of analysis will be censored at the date the participant was last known to be alive. Additional supportive unstratified analyses may also be provided.

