#### **Change from baseline**

The time point for the change from baseline will be determined based on blinded data review prior to the database lock for any PRO analysis and documented in the sSAP.

To assess the treatment effects on the PRO score, change from baseline in the global health status/QoL, physical functioning, role functioning, dyspnea, cough, chest pain, and, EQ-5D-5L VAS outcome a constrained longitudinal data analysis model proposed by Liang and Zeger [Liang, K-Y. and Zeger, S. L. 2000] will be applied, with the PRO score as the response variable, and treatment, time, the treatment by time interaction, and stratification

factors used for randomization (see Section 6.3.2) as covariates. The treatment difference in terms of LS mean change from baseline will be estimated from this model together with 95% CI. Model-based LS mean with 95% CI will be provided by treatment group for PRO scores at baseline and postbaseline time point.

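### Does Amendment 06's silence on a data cut-off and reader for the end-of-study analyses put the efficacy results at risk?

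*Combined protocol and SAP*

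**What the plan says.** The Amendment 06 list at the head of Section 9 takes effect when the investigator letter is received. On analysis it says "The pre-specified efficacy interim analysis (IA2) and final analysis outlined in the SAP will not be conducted", and then "Selected analyses of safety and endpoints will be performed at the end of the study". The same list unblinds the study, transfers MK-7684A participants to pembrolizumab, and ends submission of scans for central reading. Imaging continues under local standard of care for participants who are still treated and benefiting. On the assessor it says "All imaging as well as relevant objectives and endpoints will be assessed locally", and on vital status "There will be no follow-up for survival status".

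The list overrides earlier content, and the older text is kept for historical reference. In that older text, Section 9.4.1 defines PFS as time to "first documented disease progression per RECIST 1.1 by BICR or death due to any cause" and bases objective response on central review. Section 9.6.1.1 says that participants without a documented death "will be censored at the date the participant was last known to be alive". The only visible data restriction, in Sections 9.6.1 and 9.6.2, concerns Second Course treatment. Section 4.4 runs the study, for analysis and reporting, to the last laboratory result or the final contact, whichever is later.

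Two analysis choices were to be made blind. In Section 9.6.1, "decisions regarding the pooling will be based on a blinded review of response and event counts by stratum". In Section 9.6.3, the time point for PRO change from baseline "will be determined based on blinded data review prior to the database lock for any PRO analysis".

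**The concern.** Read literally, the end-of-study window takes in everything collected after the letter. That period differs from the rest of the trial in four ways: assignments are known, Arm 1 receives the comparator drug, scans are read locally by local methods, and deaths arrive mainly through safety reporting (Section 8.4.1: 30 days after treatment for AEs, up to 90 for SAEs).

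If all of it entered the comparison, PFS, response and duration of response would mix two assessors and two criteria. Comparator time would be credited to MK-7684A. Later OS follow-up would depend on still being on treatment, which favours patients who are doing well. Participants in survival follow-up would be frozen at their last 12-weekly contact. If strata pooling and the PRO time point were still open, they would be settled with treatment codes visible. Readers might then be unable to tell whether the choice of analyses followed the data.

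**Working it through.** **1. What the text settles.** No visible passage directs that central and local reads be combined. Under Section 9.4.1 a local read is not a PFS or response event, although a death still counts for PFS. Because the Amendment 06 list overrides older text, this does not settle the matter; it leaves it unstated. OS needs no reader, so for OS the questions are the treatment switch and the capture of deaths.

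**2. Inputs.** Event counts, power and design hazard ratios (Sections 9.7.1, 9.8 and 9.9) are redacted, so there is no planned figure to reproduce. From the documents: 1264 enrolled, 1:1 allocation, 35 cycles × 21 days = 735 days (24.15 months), contacts every 12 weeks (84 days), and study duration 5 years (month 60). Assumed: uniform accrual over 24, 30 or 34 months; letter at month 46; median time on treatment 7 months; death hazard 0.015 per month on treatment and 0.055 after early stopping. The letter month is plausible: the original protocol (19 October 2020) and Amendment 06 (29 January 2025) are about 51 months apart.

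**3. How many participants have post-letter trial data.** By simulation:

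| Accrual (months) | On treatment at letter | Share of 1264 | Pre-letter deaths after last contact | 30-month KM survival overstated by |
|---|---|---|---|---|
| 24 | 8 | 0.6% | 23 | 0.1 points |
| 30 | 36 | 2.9% | 26 | 0.6 points |
| 34 | 63 | 5.0% | 30 | 1.1 points |

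The unrecorded deaths are 2.4% to 3.7% of all deaths. With 1:1 allocation, about half of those on treatment would be in Arm 1: 63/2 ≈ 32, or 2.5%, at most. Participants in imaging follow-up go to local care, so only those still on treatment can add local reads.

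**4. Effect on the comparison.** The table describes absolute loss, but the trial asks about a ratio. Lost contacts fall on both arms alike. The scenarios were repeated with true hazard ratios of 0.81 (the external phase 3 OS result cited in Section 4.2.1.1), 1 and 1.25, comparing full ascertainment to the letter with the rules as written:

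- OS, effect unchanged after the switch: ratio of the two hazard ratios 0.998 to 1.003.
- OS, no effect after the switch: change below 0.5%.
- PFS, no effect after the switch: change below 1%.

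The sampling SD of the OS log hazard ratio is about 0.06 to 0.08. A 0.5% shift is ln(1.005) = 0.005 on that scale, and 0.005/0.06 = 0.08, so less than a tenth of one SD.

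**5. A ceiling by hand.** Let f be the share of events after the switch, with no effect from then on. The average log hazard ratio is roughly (1 − f) × ln(HR). In the 34-month scenario, total pre-letter deaths are about 30/0.037 = 811, of which 811 − 30 = 781 are captured. If all 63 treated participants then died and were counted, f = 63/(781 + 63) = 7.5%. A hazard ratio of 0.81 would become exp(0.925 × ln 0.81) = 0.823, a change of 0.823/0.81 − 1 = 1.6%. Reaching 0.863 would need f = 30%, which none of these scenarios approaches.

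**6. The blinded decisions.** Sections 9.6.1 and 9.6.3 place both in the supplemental SAP, which is not available here. Cancelling the efficacy interim removes the database lock by which strata pooling was due, but that does not show the decision is still open. ePRO collection has also stopped.

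**The case for a change.** The best case for acting does not depend on bias. Planned testing gave way to analyses chosen after futility was met, with codes open or about to be opened. Without a named list, reader and date, several defensible choices exist and can give different PFS, response and duration results. Section 9 itself expects changes to be documented before unblinding or final lock, and the Amendment 06 change table lists no such rule. Safety has the same gap: Section 9.6.2 sets aside only Second Course events, so Arm 1 events after the switch are not separated.

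What stands is that the visible text is silent. A redacted censoring table or the supplemental SAP may hold a rule, but that cannot be checked.

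Three points limit the consequence. First, no confirmatory claim remains to protect: Section 1 reports that this study met its futility criteria for OS, and IA1, the futility analysis, has been done. The end-of-study output is therefore not the only efficacy evidence. Second, Section 9 already sends changes in non-confirmatory analyses to the supplemental SAP and requires post hoc work to be labelled in the study report. Third, a final vital-status request or further central reading would change conduct as well as wording. The first runs against "There will be no follow-up for survival status", which overrides the request provided for in Section 8.11.6, and the second against the instruction to end central reading. The gain would be some 23 to 30 deaths missed at similar rates in both arms.

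**Conclusion.** No change to the plan follows. Amendment 06 leaves the cut-off, reader and endpoint list unwritten for descriptive reporting of a stopped trial. It does not prescribe pooling, and the retained definitions point to central review. An analyst would naturally stop the efficacy comparison at the letter or unblinding date, use the central reads available to then, and show later data separately.

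If the rules were instead followed literally, the OS hazard ratio would move by less than 0.5% and the PFS hazard ratio by less than 1%, with a hand ceiling of about 1.6% for OS. These sizes rest on assumed accrual, hazards, treatment duration and letter date; only accrual and the hazard ratio were varied. A much larger share of participants still on treatment at the letter would weaken the conclusion. No figure was computed for response rate or duration of response. That the blinded choices were left until after unblinding is not shown by anything in the documents.
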